- 6 Samples for central lab (including NT-proBNP) at Visit 2a need to be taken before first trial medication intake.
- 7 Women of childbearing potential only.
- 8 For patient's eligibility, local lab should be used, including a locally performed BNP or NTproBNP result taken during the current hospitalisation or in the 72 hours prior hospital admission. At the time the local BNP or NT-proBNP sample is collected, the baseline rhythm (e.g. sinus rhythm, AF) of the patient must be clarified using ECG or other measures (for example continuous heart monitoring) and documented.
- 9 In addition to the scheduled ECGs, ECGs should be done and documented at any time of clinical event (e.g. acute event of arrhythmia, tachy- or bradycardia, angina, or MI).
- 10 After the individual patient's end of the trial the investigator should only report any occurrence of cancer, related SAEs and related AESIs of which the investigator may become aware of and only via the SAE form, please see [Section 5.2.7.2.1](#).
- 11 Patients who prematurely discontinue medication are followed up according to protocol, and their visit schedule will end at their scheduled Visit 5.
- 12 Urinary pregnancy test and ECG do not need to be repeated if patient prematurely discontinued trial medication and these assessments were done at the Early Discontinuation Visit.

For potential modifications of trial conduct in case of restrictions due to COVID-19, please refer to [Sections 4.1.4, 6.1, 8.1](#) and [10.5](#).

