#### **5.1.2 NT-proBNP and BNP**

NT-proBNP or BNP measurements available from standard of care (local laboratory) will be used in all patients to determine eligibility.

NT-proBNP will be obtained at all visits from Visit 2 until Visit 5 (see Flow Chart) using central laboratory to investigate a potential effect of the trial medication.

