4. CHANGES IN THE PLANNED ANALYSIS OF THE STUDY

In the CTP, a stratified win ratio is described, but the weighting method for each stratum is not mentioned. Therefore, the weighting method to be used has been described here in [Section 7.4.1](#).

In the logistic regression models used for the binary endpoint variables (e.g. improvement in KCCQ-TSS of ≥ 10 points after 90 days of treatment), an additional continuous covariate (baseline KCCQ-TSS score) is included (see [Section 7.5.2](#)).

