7.5.2 Secondary endpoints

Other secondary endpoints are exploratory. No correction for multiple hypotheses testing will be made.

Change from baseline in continuous endpoints, such as KCCQ-TSS, will be analysed using restricted maximum likelihood estimation based on a mixed-effect model for repeated measures (MMRM) analysis to obtain adjusted means for the treatment effects. This model will include discrete fixed effects for treatment group (empagliflozin or placebo) and HF status (de novo or decompensated chronic HF) at each visit and continuous fixed effects for baseline value at each visit. Missing data caused by patient withdrawal or other reasons will be handled implicitly by the MMRM approach. An unstructured covariance structure will be used to model the within-patient errors.

Area under the curve (AUC) of change from baseline in log-transformed NT-proBNP level over 30 days of treatment will be analysed by an analysis of covariance (ANCOVA). Based on literature reviews, NT-proBNP level is regarded as log-normally distributed, therefore values will be log-transformed prior to analysis (6). The linear trapezoidal rule will be used to calculate the AUC after the log-transformation has been applied to each value.

ANCOVA with a discrete fixed effect for HF status (de novo or decompensated chronic HF) and a continuous fixed effect for baseline NT-proBNP level (log-transformed) will be used to compare treatment groups. The method of handling missing NT-proBNP levels for this analysis is described in [Section 6.6.1](#).

Comparisons between treatment groups regarding the binary endpoint variable (improvement in KCCQ-TSS of ≥ 10 points after 90 days of treatment) will be performed using a logistic regression model adjusting for the binary covariate HF status (de novo or decompensated chronic HF) and continuous covariate baseline KCCQ-TSS score. The likelihood-ratio test will be used to test for a difference between treatments. Adjusted odds ratios together with 1-sided 97.5% confidence limits will be used to quantify the effect of treatment, comparing empagliflozin to placebo as the reference.

Time to event endpoints will be analysed using the Cox proportional hazards model (7) with HF status (de novo or decompensated chronic HF) as a covariate. Hazard ratios (HRs) and their associated one-sided 97.5% confidence limits will be estimated for evaluating the superiority of empagliflozin to placebo. All time-to-event endpoints will be reported in days.

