Other secondary endpoints will be summarised descriptively [including days alive and out of hospital (DAOH)]. DAOH will be summarised as a percentage (12).

The follow-up time for DAOH analyses is defined as the minimum of 90 days after randomisation, or time between randomisation and date of censoring for non-fatal events except for patients who died within the first 90 days, where 90 days is considered as the DAOH follow-up time. Days alive and out of hospital (DAOH) for each patient is calculated as follow-up time subtracted by the number of days in hospital during the 90 days after randomisation as well as the number of days being dead within the first 90 days. Percentage DAOH is defined as DAOH divided by the DAOH follow-up time of each patient multiplied by 100.

Additionally, a negative binomial model (including HF status [de novo or decompensated chronic HF] as a factor) will be fitted to the data of recurrent HFE. The rate ratio and confidence interval will be reported.

The endpoints “diuretic effect as assessed by weight loss per mean daily loop diuretic dose after 15 days of treatment” and “diuretic effect as assessed by weight loss per mean daily loop diuretic dose after 30 days of treatment” will be defined as follows:

$$\frac{\text{Change in weight (kg) from baseline to Day T}}{\frac{\text{Mean daily i. v. dose}}{40 \text{ mg}} \text{ or } \frac{\text{mean daily oral dose}}{80 \text{ mg}} \text{ furosemide\# up to Day T}}$$

or equivalent loop diuretic dose

where the mean daily dose is defined as:

$$\frac{\sum_{x=1}^X N_x x d_x}{T}$$

and N = number of days on dose level x, d = dose level and T = day of the weight measurement.

The equivalent loop diuretic dose to a single dose of 40 mg of furosemide is defined as 20 mg of torasemide or 1 mg of bumetanide.

The dose level will be counted as 0 mg, if patients do not take loop diuretics for part of the time period. Patients not taking loop diuretics at all will be excluded from the calculation. Missing data will be handled according to the rules set out in [Section 6.6.2](#).

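### The Cox and negative binomial event models adjust only for HF status; adding baseline log NT-proBNP, already scheduled before the first dose, would be a small, nearly cost-free improvement

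*SAP*

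**What the plan says.** SAP Section 7.5.2 analyses time-to-event endpoints by a Cox model "with HF status (de novo or decompensated chronic HF) as a covariate". This covers the secondary endpoint of first CV death or HFE, and Protocol Section 7.2.3 says the same. For recurrent HFE, the SAP states that "a negative binomial model (including HF status [de novo or decompensated chronic HF] as a factor) will be fitted". Neither model has any other baseline covariate. HF status is also the only stratification factor at randomisation (Protocol Section 7.4).

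Protocol Section 5.1.2 says that "NT-proBNP will be obtained at all visits from Visit 2 until Visit 5 (see Flow Chart) using central laboratory", and a Flow Chart footnote adds that "Samples for central lab (including NT-proBNP) at Visit 2a need to be taken before first trial medication intake". SAP Section 6.7 takes the laboratory baseline from the central laboratory. In the visible text, NT-proBNP is a covariate only in the ANCOVA of its own AUC: "a continuous fixed effect for baseline NT-proBNP level (log-transformed) will be used to compare treatment groups".

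The other modelled secondary endpoints also adjust for a baseline value. The MMRM uses the baseline of its own outcome. For the logistic model of KCCQ-TSS response, SAP Section 4 records that "an additional continuous covariate (baseline KCCQ-TSS score) is included", which goes beyond the protocol.

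Secondary endpoints are exploratory (Protocol Section 7.1). Protocol Section 3.2 concedes limited power for morbidity and mortality.

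**The concern.** CV death and HFE have no baseline value of their own, so the natural counterpart to the adjustment in the other models is a marker of disease severity. One is already scheduled, log-transformed and defined at baseline, yet the two event models leave it out.

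With few events expected in 90 days, three things could be at stake: power, the size of the estimated hazard ratio, and its stability if one arm happens to be sicker at baseline. If an imbalance appeared and adjustment were chosen after unblinding, the choice would look selective.

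**Working it through.** **The plan's own figure.** The only power stated is for the primary win ratio: 87.4% with 250 patients per arm, one-sided 0.025 (Protocol Section 7.5). Simulating that section's shared-frailty model gives 87.7% at frailty variance 0.05 and 86.6% at 0.1, but only 81 to 83% at 0.5 to 4. The protocol does not state the variance. Making KCCQ-TSS independent of events gives 86.9%, so the fit to a small variance is suggestive and no more. No power, standard error or event count is stated for the event models.

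**Inputs.**
- From Protocol Section 7.5: 250 per arm, one-sided 0.025, 90-day death 5%, at least one HFE 15%, hazard ratio for HFE 0.7.
- Assumed: 18% placebo risk of the composite (between 15% and the sum of 20%); hazard ratio 0.7 for the composite and rate ratio 0.7; two thirds of patients with decompensated chronic HF, at hazard ratio 1.5; hazard or rate ratio per SD of log NT-proBNP of 1.3, 1.5 or 2.0.

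**Cox model as planned.** Schoenfeld power is Φ(|ln HR| × √(d/4) − 1.96). With d = 77.4 events: 0.357 × √19.35 = 1.569, and Φ(1.569 − 1.96) = 34.8%. With 65 to 90 events it is 30 to 39%.

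**Cox model with and without the covariate** (500 patients, 1,500 simulated trials per row; power from the mean z statistic):

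| HR per SD | SE of log HR, without → with | Mean HR, without → with | Power, without → with |
|---|---|---|---|
| 1.0 | 0.2330 → 0.2333 | 0.693 → 0.694 | 34.5 → 34.3% |
| 1.3 | 0.2330 → 0.2333 | 0.696 → 0.694 | 33.9 → 34.2% |
| 1.5 | 0.2325 → 0.2328 | 0.699 → 0.694 | 33.4 → 34.4% |
| 2.0 | 0.2325 → 0.2331 | 0.706 → 0.695 | 31.7 → 34.0% |

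The standard error rises by 0.1 to 0.3% when the covariate is added. The power gain of 0.3, 1.0 and 2.3 points comes from removing the pull of the hazard ratio toward 1. A covariate with no prognostic value costs about 0.2 points. With no treatment effect, both versions reject in about 2 to 2.5% of trials.

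**Chance imbalance.** With 250 per arm, the between-arm difference in mean standardised log NT-proBNP has SD √(2/250) = 0.089, so a two-SD imbalance is 0.179. To a close approximation the unadjusted hazard ratio becomes 0.70 × (HR per SD)^(±0.179):

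| HR per SD | Imbalance against empagliflozin | Imbalance in its favour |
|---|---|---|
| 1.3 | 0.73 | 0.67 |
| 1.5 | 0.75 | 0.65 |
| 2.0 | 0.79 | 0.62 |

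In the adjusted model this dependence is close to zero.

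**Negative binomial model.** The variance of the log rate ratio is the sum over arms of 1/(250 × I), where I is the average of μ/(1 + kμ). With the covariate, k is the frailty variance θ. Without it, k = (1 + θ)·exp(b²) − 1, where b is the log rate ratio per SD. The rate is set so that 15% of placebo patients have at least one HFE.

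| θ | SE at 1.3 per SD | SE at 1.5 per SD | SE at 2.0 per SD |
|---|---|---|---|
| 0.5 | 0.2484 → 0.2471 | 0.2497 → 0.2465 | 0.2554 → 0.2443 |
| 1 | 0.2522 → 0.2508 | 0.2541 → 0.2506 | 0.2623 → 0.2498 |
| 4 | 0.2769 → 0.2738 | 0.2825 → 0.2747 | 0.3062 → 0.2775 |

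The reduction is 0.5 to 4.8% at θ = 0.5 to 1, and up to 9.3% at θ = 4. Power rises by 0.2 to 2.3 points at θ = 1 (29.3 → 29.5% up to 27.4 → 29.7%) and by at most 3.7 points at θ = 4 (21.3 → 25.0%).

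If total overdispersion, NT-proBNP's share included, is only 0.1, little is left to gain. With variance proportional to 1/μ + k and 30% of k explained, the variance falls by 0.6% at μ = 0.2 (5.10 → 5.07) and 0.9% at μ = 0.3 (3.433 → 3.403).

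**The case against.** The strongest reply is that nothing turns on this. The endpoints are exploratory, and an analysis with about one-third power stays at about one-third. That stands, and it fixes the importance as minor.

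Second, the size is driven by an assumed prognostic strength. Entry requires raised natriuretic peptides, which narrows the covariate's range. If the small frailty variance that best matches 87.4% is right, the gains sit at the low end: 1.3 per SD alone implies a log-hazard variance of (ln 1.3)² = 0.07, and 2.0 implies 0.48. This also stands, with the caveat that the frailty variance is not stated.

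Third, the other models adjust for the baseline of their own outcome, which events do not have. A reader might infer that the SAP is inconsistent. It is not: the visible text follows one coherent rule. That rule does not make a severity covariate unsuitable, and the KCCQ-TSS entry in SAP Section 4 shows that adjustment beyond the protocol can be recorded there.

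Fourth, baseline NT-proBNP is summarised by arm (SAP Section 7.1), so an imbalance would be seen, and the unadjusted test remains valid over repeated randomisations. Seeing an imbalance is not the same as having a prespecified way to deal with it.

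Finally, the visible SAP has numbering gaps (no Section 7.6, and a gap after 7.4.1 in its contents), so an adjusted supportive analysis may exist in text that is not shown.

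**Conclusion.** The point holds as a minor improvement. Both event models adjust only for HF status, while a pre-dose central NT-proBNP is scheduled for every patient. If log NT-proBNP carries a ratio of 1.3 to 2.0 per SD, leaving it out costs about 0.3 to 2.3 points of Cox power, moves the average hazard ratio by 0.002 to 0.011 toward 1, and leaves the estimate open to chance imbalance. That imbalance is the better reason to act. In the negative binomial model the standard error is about 0.5 to 5% larger than it need be at frailty variance 0.5 to 1, less if total overdispersion is small and about 10% larger (0.3062 against 0.2775) in the most extreme case tried.

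Two stronger readings are tempting and are not supported. One is that precision is lost in the Cox model: its standard error does not shrink with the covariate, and the adjusted hazard ratio is a different, conditional quantity. The other is that the protocol forecasts a number of first events: it gives 5% deaths and 15% with an HFE separately, and no composite risk or count. The roughly 77 events used here follow from the assumed 18%.

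The primary win ratio and its 87.4% power are unaffected.

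**What to change.** In SAP Section 7.5.2, before unblinding:
- Add baseline log NT-proBNP (central laboratory, continuous) next to HF status in the Cox model for time to first CV death or HFE and in the negative binomial model for recurrent HFE.
- State that the adjusted hazard ratio is conditional on NT-proBNP.
- Replace a missing baseline value with the median of the patient's HF-status stratum, so that no randomised patient is dropped.
- Report the protocol's HF-status-only models alongside as sensitivity analyses.

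Because Protocol Section 7.2.3 fixes HF status as the Cox covariate, record the change in SAP Section 4, as was done for baseline KCCQ-TSS.

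The cost is one covariate in two models, one imputation rule and one SAP entry, with no new data. The price in interpretation is a hazard ratio that is no longer the one adjusted for HF status alone. If the sponsor prefers to keep the present models as the main ones, a prespecified adjusted supportive analysis would still give a prespecified answer to chance imbalance.

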## 5.6 OTHER ASSESSMENTS

### 5.6.1 Health Care Resource Utilisation (HCRU)

HCRU will be captured via interview with the patient and verified against medical records where available and entered in the eCRF at the visits specified in the [Flowchart](#). Information on utilization of following resources will be collected:

- All-cause hospital admissions (first and recurrent).
- Hospital admission due to worsening of heart failure (first and recurrent).
- All-cause emergency room visits (first and recurrent).
- Emergency room visits due to worsening of heart failure (requiring i.v. diuretic therapy) (first and recurrent).
- Any unscheduled outpatient visits (first and recurrent).
- Unscheduled outpatient visits related to heart failure (first and recurrent).
- Length of hospital stay(s) (initial and recurrent).
- Length of ICU stay during hospital stay (initial and recurrent).
- Intensification of diuretic therapy (adding a new diuretic, increase of dose).

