If this leads to contradictions for the start or end date of a concomitant therapy (e.g. imputed end date before documented start date), a partial end date will be imputed as the end of the interval or a partial start date will be imputed as the start of the interval in the database to resolve this contradiction.

If it is unclear from the partial date, whether a therapy was before or after date of baseline, then it will be assumed, that the therapy started after baseline (similar to worst case rules applied for adverse events).

All other cases or conflicting cases resulting from these imputation rules need to be assessed by the trial team on an individual patient basis.

Missing measurement to confirm “sustained” decrease

An eGFR (Chronic Kidney Disease Epidemiology Collaboration (CKD-EPI)cr) reduction is

considered sustained, if it is determined by two or more consecutive post-baseline central laboratory measurements separated by at least 30 days (first to last of the consecutive eGFR values). If there is no additional measurement ≥ 30 days after the eGFR reduction is observed and the patient dies within 60 days of this measurement, then the eGFR reduction is also considered sustained.

Hospital discharge date

Missing hospital discharge dates will be replaced with the date of the last follow-up.

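### A missing hospital discharge date is set to last follow-up even when later visits show the patient was out of hospital, which can give a completer 0% days alive and out of hospital (DAOH)

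*SAP*

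**What the plan says.** **Missing discharge dates.** The rule in SAP 6.6.2 is one sentence: "Missing hospital discharge dates will be replaced with the date of the last follow-up". It sets no cap and does not refer to later visits. Earlier in the same section, contradictory therapy dates are resolved, and a clause follows: "All other cases or conflicting cases resulting from these imputation rules need to be assessed by the trial team on an individual patient basis". That clause stands under concomitant therapy and non-medication therapy dates; it is not extended to discharge dates.

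**DAOH.** SAP 7.5.2 sets the follow-up time as "the minimum of 90 days after randomisation, or time between randomisation and date of censoring for non-fatal events". For patients who die within 90 days the exception is "where 90 days is considered as the DAOH follow-up time". DAOH is then "calculated as follow-up time subtracted by the number of days in hospital during the 90 days after randomisation", less any days dead. The percentage follows: "Percentage DAOH is defined as DAOH divided by the DAOH follow-up time of each patient multiplied by 100".

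**Source of the hospital data.** Protocol 5.6.1: "HCRU will be captured via interview with the patient and verified against medical records where available". Protocol 8.3.1 makes onset dates of adverse and outcome events mandatory, but asks for end dates only where they exist.

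**Role.** Protocol 2.1.3 lists DAOH twice as a secondary endpoint: once to 90 days after randomisation, and once with a window closing 30 days after the initial discharge. Hospitalisation for heart failure (HHF) has the same 30-day post-discharge window. Protocol 7.2.3 and SAP 7.5.2 make DAOH descriptive.

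**The concern.** The discharge rule can contradict the trial's own data. A patient who walks into the clinic on Day 15 was not in hospital that day, yet the rule keeps the patient there until last follow-up if the discharge date was never recorded. DAOH is meant to show days lost to death and hospital. Under this rule it would also reflect how complete the discharge records are, and those depend partly on patient interview and on records from other hospitals.

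The effect is not confined to 90-day DAOH. If the initial discharge is moved to last follow-up, a window defined as 30 days after that discharge covers the patient's whole observed follow-up. An HHF late in follow-up would then count as an early post-discharge event.

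A second, weaker feature lies in the denominator. Every patient is randomised while still in hospital (Protocol 3.3.2, criterion 6), so hospital days come first. When follow-up is cut short, the index stay takes up a larger share of the observed time.

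**Working it through.** The documents give no numerical DAOH figure to reproduce, so the SAP formula is applied directly.

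**Inputs from the documents**
- Percentage DAOH = 100 × (F − H − D)/F, where F is follow-up time, H is hospital days after randomisation and D is days dead (SAP 7.5.2).
- F = min(90, day of non-fatal censoring), or 90 if the patient died within 90 days (SAP 7.5.2, 6.8.3).
- Visits 3, 4 and 5 are on Days 15, 30 and 90, with a window of ±3 days at Visit 3 (Protocol flow chart, 6.2.2).
- 250 patients per arm (Protocol 7.5).

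**Assumptions.** The documents give neither the length of stay nor the day of censoring. A 5-day index stay after randomisation is used unless stated otherwise.

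**1. Completer with a missing index discharge date, seen at Visits 3 to 5**
- True value: (90 − 5)/90 = 94.4%.
- SAP rule: discharge is set to last follow-up, so H = 90 and the score is (90 − 90)/90 = 0%.
- Effect on the arm mean: 94.4/250 = 0.38 points per patient; five such patients give 1.9 points.
- Stay ended on the day before a Day 15 visit: (90 − 14)/90 = 84.4%. Over the Day 12 to 18 window this runs from 87.8% to 81.1%. It still overstates the stay, but far less.

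**2. Readmission on Day 20, no discharge date, seen on Days 30 and 90**
- SAP rule: about 70 days counted (Days 20 to 90).
- Consistent with the visits: at most about 10 days (Days 20 to 30).
- Excess: about 60 days, or 60/250 = 0.24 days on the arm mean.

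**3. Windows closing 30 days after the initial discharge.** With discharge set to last follow-up, the window closes 30 days after the patient was last observed, so it covers all observed time. This applies to the second DAOH endpoint and to HHF occurrence.

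**4. Own-follow-up denominator (secondary point).** Score (F − 5)/F for a patient censored alive on day F:

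| F | 5 | 8 | 10 | 15 | 30 | 60 | 90 |
|---|---|---|---|---|---|---|---|
| % DAOH | 0 | 37.5 | 50.0 | 66.7 | 83.3 | 91.7 | 94.4 |

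The stay matters as much: at F = 10 the score is 80% for H = 2, 70% for H = 3 and 30% for H = 7.

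Effect on an arm mean, with assumed withdrawal rates:
- 5% withdrawn, all on Day 10: 0.95 × 94.4 + 0.05 × 50 = 92.2%, a fall of 2.2 points.
- 5% in one arm and 2% in the other, all on Day 10: 0.03 × (94.4 − 50) = 1.3 points, or 1.2 days of 90.
- The same rates, withdrawals spread evenly over Days 5 to 90: the mean of (F − 5)/F is 82.56%, so the difference is 0.03 × (94.44 − 82.56) = 0.36 points, or 0.3 days.
- Person-day weighting, 5% withdrawn on Day 10: (0.95 × 85 + 0.05 × 5)/(0.95 × 90 + 0.05 × 10) = 81/86 = 94.19%, a fall of 0.26 points instead of 2.2.

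**The case against.** The discharge-date problem may be rare. Protocol 5.6.1 collects length of stay, initial and recurrent, and the flow chart schedules that interview at Visits 3, 4 and 5, so a patient who attends can be asked again. The index discharge should be well documented, because the patient is in hospital at randomisation and receives the take-home kit at discharge (Protocol 6.2.2). The documents give no frequency. All of this stands. It limits the expected size but does not make the rule right when it is invoked.

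DAOH is descriptive, with no test, model or place in a hierarchy. SAP 7 also reports medians and quartiles, which a few extreme scores hardly move. This stands too and sets the severity.

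On the denominator, a reader might infer that the rules turn a withdrawer's missing time into hospital time, or that an early withdrawer scores near 50%. The documents support neither. Unobserved days leave both numerator and denominator; none is counted as hospitalised. A score near 50% needs follow-up of about twice the hospital stay. Nor does stopping study drug shorten follow-up: Protocol 3.1 and 3.3.4.1 keep these patients to Day 90, so only consent withdrawal and loss to follow-up matter. The 1.3-point difference between arms puts every withdrawal on Day 10; spreading them evenly brings it to about 0.36. Scaling to own follow-up is a defensible choice, and the SAP cites a published method for its percentage.

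**Conclusion.** The discharge-date rule needs correcting. As written it is unconditional, and it gives a wrong answer whenever a later contact shows the patient was out of hospital: 0% instead of 94.4% for a completer with an unknown index discharge date, and about 60 false hospital days in the readmission example. These sizes rest on the assumed 5-day stay and on the illustrated dates. The effect on an arm mean depends on how many discharge dates are missing, which cannot be known from the documents.

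The denominator point holds in mechanism only. The index stay is overweighted in patients censored early, by an amount that depends on stay and censoring day. It justifies a sensitivity summary, not replacement of the planned analysis.

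Overall the point is minor. DAOH is descriptive, and neither the primary test nor any other confirmatory conclusion is affected.

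**What to change.** **Main change, SAP 6.6.2.** Replace the discharge-date sentence with: *missing discharge date = the day before the first documented out-of-hospital contact after that admission; if there is none, date of last follow-up.* State which records count as such a contact, for example an attended clinic or outpatient visit; a phone call alone does not show where the patient was. Apply the same date to the two windows that close 30 days after the initial discharge.

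**Optional addition, SAP 7.5.2.** Add a person-day-weighted sensitivity summary per arm: total DAOH days divided by total follow-up days. Keep the planned per-patient summary on all randomised patients. Restricting it to deaths and complete follow-up would condition on a post-randomisation outcome and depart from the all-randomised basis of the efficacy analyses. Person-day weighting is also a different summary, an arm-level ratio, so it should stand beside the planned one and not replace it.

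**Cost.** SAP wording and minor programming on data already collected. No change to trial conduct, sample size or the primary analysis.
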